1 BACKGROUND INFORMATION

Nonalcoholic fatty liver disease (NAFLD) is the most common cause of chronic liver disease worldwide (Vernon et al., 2011), and is estimated to occur in 30-40% of adults in the United States and up to 30% of European adults. These numbers approach 95% in those with morbid obesity (Mathus-Vliegen et al., 2012). NAFLD ranges from simple steatosis, which is typically nonprogressive, to nonalcoholic steatohepatitis (NASH), which has a 20% likelihood of progression to advanced disease including fibrosis, cirrhosis and its complications including liver failure and the need for a liver transplant (Angulo, 2002). Hepatocellular carcinoma is also a complication of NASH that may occur with or without the presence of cirrhosis (Torres et al., 2012). NAFLD is typically associated with type 2 diabetes mellitus (T2DM) (Adibi et al., 2007; Loomba et al., 2012), central or visceral obesity (Souza et al., 2012), dyslipidemia (Assy et al., 2000; National Cholesterol Education Program, 2002), and hypertension (Donati et al., 2004). Together these conditions comprise the metabolic syndrome, and NASH is considered to be the hepatic component of this syndrome (Hamaguchi et al., 2005; Neuschwander-Tetri, 2005; Marchesini et al., 2005). Notably, NAFLD is a clinical condition occurring in individuals who do not drink excessive alcohol (>20 grams/day), yet have hepatic histology which is indistinguishable from that seen with alcoholic excess. The pathophysiology of NASH is likely multifactorial and may include combinations of metabolic, genetic, environmental, and gut microbial factors.

Most individuals with NASH are asymptomatic or have nonspecific symptoms such as fatigue. They typically first come to medical attention incidentally following routine blood testing or on imaging studies performed routinely or during the evaluation of an unrelated condition. While ultrasound and magnetic resonance imaging (MRI) can detect the presence of steatosis (Reeder et al., 2011), a liver biopsy is required to diagnose NASH and the extent of liver fibrosis.

1.1 Indication and Current Treatment Options

There are currently no drugs approved for the treatment of NASH and it is estimated that there are between 6-16 million people in the United States with NASH, of which 600,000 have severe disease (Williams et al., 2011 and Torres and Harrison, 2008), with similar percentages reported throughout most areas of the world (World Gastroenterology Organisation, 2012). Treatment of associated metabolic comorbidities, weight reduction, and incorporation of an exercise routine remain the cornerstone of management. However, lifestyle changes are seldom successful. Thus, NASH represents a disease with an unmet medical need that is growing at an epidemic rate, and that if untreated, carries a risk of significant morbidity and mortality.

1.2 Product Background and Clinical Information

Volixibat potassium (SHP626; formerly LUM002), hereafter referred to as volixibat, is a highly selective inhibitor of the apical sodium-dependent bile acid transporter (ASBT) that is being evaluated for the treatment of NASH.

Bile acids (BA) promote bile flow, activation of digestive enzymes, and micellization of fats and fat-soluble vitamins, thereby permitting their intestinal absorption. BAs serve as signaling molecules acting via receptors, such as farnesoid X receptor (FXR) and transmembrane G protein-coupled receptor (TGR5), in the intestine, liver and other tissues which play an important role in regulating insulin homeostasis. (Halilbasic et al., 2013). Lipid peroxidation and oxidant stress have been proposed as one link between the accumulation of fat and subsequent injury (Day and James, 1998). All of these metabolic actions have important effects to prevent the ongoing liver damage in NASH.

High fat diet (HFD) fed mice treated with an ASBT inhibitor (ASBTi) (SC-435 a surrogate SHP626) normalized hepatic triglycerides and serum cholesterol, significantly improved insulin resistance (IR), and decreased NAS, predominantly steatosis. In addition the BA pool reflected increases in BA that were agonists to FXR and decreases in levels that were antagonist to the FXR (Rao et al., 2016). Miethke and colleagues found that pharmacological inhibition of the ileal, ASBT (SC-435 the surrogate molecule of volixibat), blocked progression of sclerosing cholangitis in mdr2^{-/-} mice (Miethke et al., 2016). Beneficial effects in liver histology in these mice included a reduction in the severity of hepatic fibrosis, a decrease which correlated with a reduction of hepatic profibrogenic gene expression. While very encouraging, whether or not the findings in this mouse sclerosing cholangitis model can translate to histologic improvements in patients with NASH is unknown.

Volixibat, as a potent inhibitor of ASBT, increases BA excretion and facilitates signaling in the intestine that regulates serum and hepatic BA concentrations, glucose metabolism, serum cholesterol and fatty acid metabolism in the liver. The combined events resulting from inhibiting BA reuptake are hypothesized to have a positive metabolic, anti-inflammatory, anti-steatotic, and potentially antifibrotic effect that will lead to a therapeutic benefit for patients with NASH.

One of the factors contributing to the pathogenesis of NASH is abnormal cholesterol metabolism and the accumulation of free cholesterol in the liver. The free cholesterol is directly toxic to hepatocytes, which leads to inflammation and fibrosis (Musso et al., 2013). One treatment approach is to remove the cholesterol from the liver to decrease and possibly reverse the damage to the hepatocytes. This is one of the mechanisms by which SHP626 will treat NASH.

Due to the mechanism of action (MOA), volixibat is under development for the treatment of NASH and may also be able to improve the metabolic syndrome that is associated with NASH. Volixibat inhibits ASBT therefore BAs are excreted in the feces and this loss forces the liver to synthesize new BA which utilizes cholesterol in the liver and serum. Volixibat also has the potential to reduce IR, which is considered to be the most common underlying risk factor for the development of NASH (Pagano et al., 2002; Sanyal et al., 2001).

Volixibat was initially being evaluated for its use as an intervention for dyslipidemia. As a result of initial observations in animals that serum low-density lipoprotein cholesterol (LDL-C) and total liver cholesterol content could be decreased after administration of volixibat, additional work was undertaken to support the safety and tolerability of the drug in healthy volunteers. Clinical and non-clinical studies have demonstrated very low systemic exposure across species.

Oral administration of volixibat at doses up to 300 mg once daily and 50 mg administered daily for 14 days to healthy male subjects was generally safe. A Phase 1 study revealed that volixibat is tolerated at the 10 mg dose for 28 days and that there were trends towards increasing high-density lipoprotein cholesterol (HDL-C), decreasing LDL-C, and decreasing fasting glucose in patients with T2DM (LUM002-101 trial).

A healthy volunteer study investigating 12 days of varying levels of repeat doses of volixibat has provided key pharmacodynamic information for dose selection as measured by the effect of volixibat on excreted fecal bile acid (FBA) levels (SHP626-101). In addition, the study investigated safety and tolerability over the dose range that was considered for this Phase 2 study.

Data from Phase 1 studies support the position that volixibat is basically a non-absorbed drug that works locally in the GI tract and results in virtually no systemic exposure. Thus pharmacokinetic sampling will not be done in this study.

The current proof of concept (POC) Phase 2 trial will evaluate the safety, tolerability, and efficacy of three doses of volixibat (5, 10, and 20 mg) in adult subjects with NASH. Due to the MOA of volixibat, efficacy will be assessed at an interim analysis (IA) by a change of steatosis from baseline to Week 24 compared to placebo (PBO). While the gold standard for quantification of steatosis has historically been an invasive liver biopsy, quantitative magnetic resonance (MR) imaging-based biomarkers for liver fat have evolved rapidly over the last decade, and are increasingly being incorporated into NASH clinical trials. Both MR spectroscopy (S) and MR imaging (I) proton density fat-fraction (PDFF) provide non-invasive means of quantifying intrahepatic lipid content (Reeder et al., 2012). Both techniques have been shown to be accurate, reproducible with a low degree of variability in interpretation, cost-effective and reliable biomarkers of quantitative hepatic fat (Roldan-Valadez et al., 2010; Urdzik et al., 2012; Raptis et al., 2012). Importantly, studies demonstrate a close correlation with steatosis grade histologically (Qayyum et al., 2005; Schwenzer et al., 2009).

In a study of 51 adult subjects with NAFLD, PDFF correlated well with the grade of histologic steatosis, as the mean fat-fraction values of 8.9%, 16.3%, and 25.0% corresponded to histologic steatosis grades 1, 2, and 3, respectively ($P < .0001$) (Permutt et al., 2012). Thus, MRI will be utilized to evaluate the degree of steatosis change from baseline in this study during the IA. The Mozart trial was a randomized, double-blind, PBO-controlled trial of 50 patients with NASH who were randomized to 24 weeks of either ezetimibe or PBO, evaluating the reduction of liver fat by MRI-PDFF as well as by histology. Results revealed that compared to histologic non-responders, histologic responders, defined as a two-point reduction in NAFLD activity score (NAS) without worsening fibrosis, had a statistically significant reduction in net MRI-PDFF of $-4.1\% \pm 4.9$ vs. $+0.6\% \pm 4.1$ ($P < 0.036$) with a mean percent change of $-29.3\% \pm 33.0$ vs. $+2.0\% \pm 24.0$ ($P < 0.004$), respectively (Loomba et al., 2015). Thus, in the current trial during the IA, a $\geq 5\%$ steatosis reduction for an active dose compared to PBO will be a clinically meaningful change after 24 weeks of therapy.

Intrahepatic lipid content of less than 1% is considered to be within the normal range ([Springer et al., 2015](#)), however, from a study of 2349 people in a general population undergoing MRS, it was concluded that a PDFF value of 5.56% represented the upper limit of the normal range, as determined from the 95th percentile of PDFF in 345 individuals who were not at increased risk for hepatic steatosis ([Szczepaniak et al., 2005](#)). Thus, in the current trial, similar to other NASH trials utilizing MR for evaluation, an MRI $\geq 5\%$ steatosis will be used as an inclusion criterion ([Loomba et al., 2015](#)).

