9.5 Planned Interim Analysis and Data Monitoring Committee

9.5.1 Planned Interim Analysis

The IA will be conducted after at least 80 subjects have received 24 weeks of treatment. To protect study integrity, the IA will be performed by an independent statistician and statistical reporting group as well as a gastroenterologist and hepatologist who are not involved in the clinical trial conduct and are not responsible for the final analysis of clinical trial data. The IA will be performed to evaluate the safety, tolerability, and efficacy of 3 doses of volixibat each compared to PBO and may be used to drop 1 or 2 doses of volixibat, or to terminate the trial.

The criteria for deciding whether or not to continue randomizing to a particular volixibat dose following the Week 24 IA will be specified in the DMC charter. In general, randomization to any volixibat dose determined to be unsafe, intolerable or ineffective/futile at the IA will be discontinued. If all of the volixibat doses are determined to be intolerable or ineffective/futile the clinical trial will be terminated. If none of the volixibat doses are determined to be unsafe, intolerable or ineffective/futile then randomization to the volixibat dose that is the least promising or least helpful in characterizing the dose-response relationship (as specified in the DMC charter) may be discontinued. Tolerability will be assessed by comparing the number of discontinuations due to any one TEAE (presumably gastrointestinal events, most notably, diarrhea, loose stools, increased evacuations, and abdominal pain) between each volixibat dose group and PBO group. Efficacy will be assessed based on a reduction of steatosis (assessed by MRI-PDFF) and ALT by comparing the change from baseline in MRI-PDFF and percent change from baseline in ALT at Week 24 between each volixibat dose group and PBO group.

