9.6 Sample Size Calculation and Power Considerations

These are the primary hypotheses that are being tested in this study:

- Null: The proportion of subjects at Week 48 with a reduction of at least 2 points without worsening of fibrosis from baseline NAS does not differ between any of the volixibat doses and PBO.
- Alternative: The proportion of subjects at Week 48 with a reduction of at least 2 points without worsening of fibrosis from baseline NAS does differ between at least one volixibat dose and PBO.

Response rates of 21% (PBO) and 45% (active) were reported in the FLINT trial ([Neuschwander-Tetri et al., 2015](#)) using the same primary end-point of reduction of NAS by at least two points (without worsening of fibrosis). Based on those response rates, 67 subjects per group completing the trial are needed for 80% power with a 10% type I error. Holm multiplicity adjustment was included in the sample size estimate.

Approximately 899 subjects will be screened to randomize 292 subjects to achieve 201 completers in the three arms (2 volixibat and 1 PBO) that continue after the IA (one dose is dropped at the IA); approximately 807 subjects will be screened to randomize 260 subjects to achieve 134 completers in the two arms (1 volixibat and 1 PBO) that continue after the IA (two

doses are dropped at the IA). After randomization of at least 80 subjects (20/treatment arm), a 24-week IA may eliminate at least one active dose group based on the criteria provided to the DMC. The sample size target for this study is 67 completers in each of the treatment groups that were not dropped at the IA (201 total if 3 arms continue, 134 if 2 arms continue). Accounting for a 20% dropout, 81 subjects will be randomized in each of the treatment groups that continue. Including the projected approximately 49 additional subjects randomized to a dose that is dropped at the IA, 292 subjects (81 for each arm that continues + 49 in the dropped arm) will be randomized if 3 arms (2 volixibat and 1 PBO) continue; 260 subject (81 for each arm that continues + 49 for each of the dropped arms) will be randomized if 2 arms (1 volixibat and 1 PBO) continue. Should the number of subjects randomized prior to the IA to a dose group that is dropped at the IA markedly deviate from the above projection, then the total number of subjects randomized will be adjusted accordingly, not to exceed approximately 324 subjects.

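### Section 1.2 takes its interim PDFF benchmark (≥5%, active dose versus placebo) from a responder/non-responder gap, not from a difference between arms, and does not state the scale

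*Protocol*

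**What the plan says.** Section 1.2 (Product Background and Clinical Information) summarises a 24-week placebo-controlled ezetimibe trial in 50 patients with NASH. The comparison it reports is "compared to histologic non-responders, histologic responders, defined as a two-point reduction in NAFLD activity score (NAS) without worsening fibrosis". The mean absolute PDFF change was -4.1 points (SD 4.9) in responders and +0.6 (SD 4.1) in non-responders. The mean percent change was -29.3% (SD 33.0) and +2.0% (SD 24.0). The next sentence, introduced as a consequence, says that at this trial's interim analysis a ≥5% "steatosis reduction for an active dose compared to PBO will be a clinically meaningful change after 24 weeks of therapy". It does not say whether 5% means PDFF points or percent change.

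Section 9.6 sets the planned effect: "Response rates of 21% (PBO) and 45% (active) were reported in the FLINT trial".

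Section 9.5.1 leaves the criteria for continuing a dose to the DMC charter and adds that, in general, "randomization to any volixibat dose determined to be unsafe, intolerable or ineffective/futile at the IA will be discontinued". The trial is terminated if all doses are found intolerable or ineffective/futile. Efficacy at the interim is to be judged on the change from baseline in MRI-PDFF *and* the percent change from baseline in ALT. The synopsis (Planned Interim Analysis) says steatosis *or* ALT.

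**The concern.** A treatment arm is a mixture of responders and non-responders. The gap between those two kinds of patient is therefore the largest arm difference that the cited figures could produce, reached only if everyone responds on active and nobody on placebo. Using that gap, rounded up, as the meaningful difference between arms sets a benchmark that does not fit the response rates on which the trial is powered.

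The interim look can stop randomization to a dose or end the trial, and ≥5% is the only numeric interim efficacy benchmark found in the protocol. If it carries into the charter, doses with the intended histologic effect could be judged ineffective on the PDFF part of the decision.

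**Working it through.** **The plan's own figure.** Section 9.6 states "67 subjects per group completing the trial are needed for 80% power with a 10% type I error", with Holm included. Two doses give a first Holm step of 0.10/2 = 0.05, two-sided. With p = 0.21 and 0.45 (mean 0.33):

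- Uncorrected n = [1.96 × √(2 × 0.33 × 0.67) + 0.842 × √(0.21 × 0.79 + 0.45 × 0.55)]² / 0.24² = 59.1, or 60 per group.
- With continuity correction, n = (59.1/4) × [1 + √(1 + 4/(59.1 × 0.24))]² = 67.1, or 68 rounded up. Corrected power at 67 is 79.9%.

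The 67 therefore reproduces, and 45% versus 21% is the effect to test the benchmark against.

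**Inputs for the benchmark.** Responder and non-responder means and SDs come from Section 1.2, response rates from Section 9.6, and 20 per arm at the interim from Sections 3.1 and 9.6. *Assumptions, not in the protocol:* PDFF moves only through the responder share; the ezetimibe trial's means and SDs carry over; Week 48 response rates apply at Week 24; the observed difference is approximately normal.

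**Absolute reading.**

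- Gap = 0.6 - (-4.1) = 4.7 points.
- 100% versus 0% responders: expected arm difference 4.7, below 5. 100% versus 21%: 0.79 × 4.7 = 3.7.
- 45% versus 21%: 0.24 × 4.7 = 1.13.
- Active variance = 0.45 × 4.9² + 0.55 × 4.1² + 0.45 × 0.55 × 4.7² = 25.5 (SD 5.05).
- Placebo variance = 0.21 × 4.9² + 0.79 × 4.1² + 0.21 × 0.79 × 4.7² = 22.0 (SD 4.69).
- SE = √((25.5 + 22.0)/20) = 1.54.
- P(observed ≥5) = P(Z > (5 - 1.13)/1.54) = P(Z > 2.51) = 0.6%.
- With a common SD from 4 to 8 points instead, the probability runs from 0.1% to 6.3%.

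**Absolute reading, drug lowering fat directly.** With a common SD of 4.85, SE = 4.85 × √(2/20) = 1.53.

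| True arm difference (points) | P(observed ≥5) |
|---|---|
| 3 | 10% |
| 4 | 26% |
| 5 | 50% |

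**Relative reading.**

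- Gap = 31.3%; expected difference = 0.24 × 31.3 = 7.5%.
- Mixture SDs by the same formula: 32.4 (active) and 29.1 (placebo). SE = √((32.4² + 29.1²)/20) = 9.7.
- Effective dose: P(observed ≥5%) = P(Z > (5 - 7.5)/9.7) = 60%.
- Inert dose (21% in both arms): SE = 29.1 × √(2/20) = 9.2; P(Z > 5/9.2) = 29%.

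**Which scale?** Section 9.5.1 specifies change from baseline for PDFF and, in the same sentence, percent change for ALT. The absolute gap of 4.7 is also close to 5, while the relative gap is 31.3. Both favour absolute points, but neither settles it.

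**The case against.** A reader might infer that a dose with the planned effect *would be dropped as futile*. The documents do not support that. Section 1.2 is background and calls ≥5% clinically meaningful; it does not call it a futility bound. Section 9.5.1 never cites 5% and sends the criteria to a charter that is not shown. A charter might apply the figure through a confidence interval or a predictive probability, which would change the probabilities. ALT also counts: under the synopsis's *or*, missing the PDFF mark would not by itself make a dose ineffective. The DMC recommends and the sponsor decides (Section 9.5.2), and subjects already on a dose dropped for futility continue it.

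A reader might also take 0.6% as settled. It is not: the protocol plans a histologic effect at Week 48 and states no PDFF effect. Section 1.2 chooses steatosis because of the mechanism of action, and the mouse data it cites show a mainly steatotic improvement, so fat may fall directly. The same section gives mean PDFF of 8.9%, 16.3% and 25.0% for steatosis grades 1, 2 and 3, or 7.4 to 8.7 points per grade, which makes 5 points look less remote.

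All of this stands as a limit on the claim. It does not repair the derivation. The sentence is worded for use at this trial's interim analysis, and the contrast behind it is between types of patient. Five points net of placebo is 56%, 31% and 20% of those three grade means, against an average fall of 29.3% in the cited responders. Under the *and* of Section 9.5.1, failing on PDFF could be decisive.

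**Conclusion.** The benchmark rests on the wrong contrast and its scale is undefined. That much follows from Section 1.2 alone. On the absolute reading it lies above the 4.7 points that complete separation of responders would give, and more than four times above the 1.1 points implied by 45% versus 21%. The 1.1 points and the 0.6% hold only under the assumptions listed with the calculation; a direct effect on fat raises the chance to 10–50% for true differences of 3 to 5 points. On the relative reading the benchmark is attainable but separates poorly, at 60% against 29%. Whether any dose would be lost depends on the charter: the harm arises if it uses this figure for the PDFF part of the efficacy or futility decision.

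**What to change.** - In Section 1.2, state the scale. Describe 4.7 points only as a responder/non-responder difference. Replace ≥5% with an arm-level benchmark consistent with 45% versus 21%, and state its assumptions (mechanism, source of means and SDs, timing).
- Reconcile *steatosis or ALT* in the synopsis with PDFF *and* ALT in Section 9.5.1.
- Confirm that the DMC charter criterion matches, and report its probability of keeping a dose with the planned effect and of keeping an inert dose.

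The choice of futility bound belongs to the sponsor and the DMC. Continuing any dose with some observed reduction versus placebo is not recommended as such. At 20 per arm it keeps a dose with the 1.13-point effect about 77% of the time (P(Z > -1.13/1.54)), but an inert dose about 50%. With three inert doses sharing one placebo arm of equal size and variance, at least one survives about 75% of the time (1 - 1/4, by symmetry).

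The cost is a few sentences in Section 1.2, one word in the synopsis or Section 9.5.1, and a check of the charter. A lower benchmark keeps inert doses more often, which is why both probabilities should be reported.

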1.3 Benefits and Risks

By virtue of volixibat's ability to inhibit ASBT bile acid reabsorption, there is an increase in BA excretion and signaling in the intestine that results in improvements in glucose metabolism and changes in cholesterol and fatty acid synthesis in the liver. Recently, HFD fed mice treated with an ASBTi (SC-435 a surrogate of SHP626) normalized hepatic triglycerides and serum cholesterol, significantly improved IR, and decreased NAS (predominantly steatosis). In addition, these HFD-fed mice did not gain weight when treated with SC-435, in spite of consuming increased calories. Finally, the BA pool in these mice changed to predominantly FXR agonist ([Rao et al., 2016](#)).

These metabolic actions and preclinical results may prove to be clinically relevant to subjects with NASH.

NASH has recently received considerable attention as awareness of the problem of liver damage and prevalence of the disorder has increased, paralleling the obesity epidemic. Consequences of liver damage are detrimental and can lead to liver failure, hepatocellular carcinoma, and the need for liver transplantation. There is no currently approved medical therapy for NASH. The large unmet medical need and the increased medical resource burden have led to the search for potential therapies to treat NASH.

Nonclinical testing established that the no observed adverse effect level (NOAEL) for volixibat in rats and dogs following 13 weeks of once-daily administration were 1000 and 500 mg/kg/day, respectively. Similarly, testing confirmed that the NOAEL for volixibat in a 6-month study in rats and a 9-month study in dogs were 1000 and 500 mg/kg/day, respectively. In both cases, these were the highest doses tested. Genotoxicity testing has yielded negative findings.

Volixibat is minimally absorbed ([Siebers et al., 2017](#)). The pharmacokinetic profiles performed in clinical studies completed to date repeatedly suggest negligible systemic exposure. Furthermore, there has been no observation of clinically relevant changes in fat absorption parameters such as those related to fat-soluble vitamins.

The most frequent TEAEs in the Phase 1 studies were GI and were considered mechanism-based due to elevated BA concentrations in the colon. The percentage of subjects reporting at least 1 TEAE in the GI disorders SOC generally increased with an increasing volixibat dose level (Part 1 Study TDU10632 and Study LUM002-101). Most TEAEs were mild in intensity, and none were assessed as severe.

In the multiple dose studies, the most commonly reported TEAEs in subjects (both healthy and with T2DM) who received volixibat for the longest duration of 28 days in Study LUM002-101 included diarrhea and abdominal pain. The most commonly reported TEAEs in subjects receiving 50 mg volixibat for 14 days (part 3 Study TDR10633) were diarrhea and GI pain.

Overall, there were 2 SAEs (ALT increased and retinal detachment), both of which led to the discontinuation of volixibat. In part 3 of the initial Phase 1 study (TDU10633), 1 subject dosed with 50 mg volixibat for 13 days was withdrawn from the study due to a mild TEAE (which became a SAE due to prolonged hospitalization) of ALT increased that was considered related to volixibat. The subject's ALT level returned to normal after discontinuation of volixibat. A second subject dosed with 10 mg volixibat for 12 days in Study LUM002-101 reported a moderate SAE of ablation of the retina with a bleed in the vitreous body of the right eye that was considered not related to volixibat.

Overall, 3 subjects, all dosed with 5 mg volixibat in Study LUM002-101, discontinued volixibat due to non-serious TEAEs: 1 due to a related TEAE of mild hemorrhagic diarrhea, 1 due to an unrelated TEAE of moderate Epstein-Barr virus infection, and 1 due to mild related TEAEs of diarrhea and anal erosion.

Overall, the observed AEs attributable to volixibat have been self-limited as would be expected given the local MOA of ASBT inhibition in the terminal ileum. Generally, among subjects who experienced GI TEAEs, the events have been mild and diminished over the course of treatment. Please refer to the investigator's brochure for additional information.

Volixibat is a novel drug candidate, demonstrating limited systemic exposure across species with the potential to affect important metabolic pathways associated with NASH. The overall safety, tolerability, and preliminary activity of volixibat in available clinical trials suggest that further investigation is warranted and that there is a positive benefit to risk profile.

Always refer to the latest version of the Volixibat Potassium (SHP626) Investigator's Brochure for the overall risk/benefit assessment and the most accurate and current information regarding the drug metabolism, pharmacokinetics, efficacy, and safety of volixibat.

See [Appendix 1](#) for protocol history, including all amendments.

